APPENDIX E DESIRABILITY APPROACH

- **DERIVED ENDPOINTS**

The following endpoints will be computed and taken into account in the desirability analysis:

1. Incidence rate of any Grade 2 and any Grade 3 general AE (solicited and unsolicited) and any vaccine-related SAE during the 7-day follow-up period after vaccination for each investigational RSV vaccine formulation.
2. Incidence rate of Grade 2 and Grade 3 fever during the 7-day follow-up period after vaccination for each investigational RSV vaccine formulation.
3. Geometric mean of neutralising antibody titres against RSV-A at Day 30 adjusted for pre-vaccination titres.
4. Geometric mean of PCA concentrations at Day 30 adjusted for pre-vaccination titres.

- **STATISTICAL COMPUTATION**

Reactogenicity

[figure not shown]
A logistic regression model will be fitted on each reactogenicity endpoint (any Grade 2/3 general AE and any related SAE, Grade 2/3 fever) reported during the 7-day follow-up period after vaccination, including all RSV formulations.

For any Grade 2/3 general AEs and any related SAEs, the incidence rate estimate (**IR**) will be transformed in a [0,1] desirability index using the following function:

$$DR1 = \begin{cases} \frac{1}{1 + \exp(-50 * (0.25 - IR))}, & \text{if } IR \leq 0.25 \\ - \\ \frac{1}{1 + \exp(-25 * (0.25 - IR))}, & \text{if } IR \geq 0.25 \end{cases}$$

where **IR** is the incidence rate estimated by the model. This function will allocate a desirability value of 1, 0.5 and 0 to incidence rate equal to 0.1, 0.25 and 0.5 respectively (see [Figure 3](#)).

Figure 3 Desirability function for the incidence rate of Grade 2/3 general AEs and related SAEs - for each investigational RSV vaccine formulation

[figure not shown]

For Grade 2/3 fever, the incidence rate estimate (**IR**) will be transformed in a [0,1] desirability index using the following function:

$$DR2 = \frac{1}{1 + \exp(-120 * (0.05 - \mathbf{IR}))}$$

where **IR** is the incidence rate estimated by the model. As illustrated in [Figure 4](#), the function will allocate desirability values of 1, 0.5 and 0 to incidence rate equal to 0, 0.05 and 0.1 respectively.

Figure 4 Desirability function for the incidence rate of Grade 2/3 fever - for each investigational RSV vaccine formulation

Finally, the reactogenicity index will be computed by taking the geometric mean of the 2 indexes:

$$DR = \sqrt{DR1 * DR2}$$

Immunogenicity

A response-surface model will be fitted on the log-transformed titre for each immune response (neutralising anti-RSV-A and PCA), including all RSV formulations.

As formulations inducing a high immune response will be considered suitable, the lower limit (LL) of the estimated GMT/C adjusted for pre-vaccination titres will be the statistical criterion considered for decision making.

[figure not shown]
Neutralising anti-RSV-A titres

The LL of the GMT estimate will be transformed into a [0,1] desirability index using the function:

$$DI1 = \frac{1}{1 + \exp(1.5 * (9.5 - LL))}$$

where LL is the lower limit of the 95% confidence interval of the GMT adjusted for pre-vaccination titres in log base 2. The function was chosen to have a desirability of 0 at LL value $\leq 6 \log_2$ (=128), and a desirability of 1 at LL value $\geq 13 \log_2$. This function is illustrated in [Figure 5](#).

Figure 5 Desirability function for neutralising anti-RSV-A GMTs - for each investigational RSV vaccine formulation

[figure not shown]
PCA concentrations

The LL of the GMC adjusted for pre-vaccination titres estimate will be transformed using the following function:

$$\text{DI2} = \begin{cases} \frac{1}{1 + \exp(0.05 * (150 - LL))}, & \text{if } LL \leq 150 \\ \frac{1}{1 + \exp(0.025 * (150 - LL))}, & \text{if } LL \geq 150 \end{cases}$$

As illustrated in [Figure 6](#), a PCA response of 25, 150 and 400 µg/mL will have a desirability value of 0, 0.5 and 1 respectively.

Figure 6 Desirability function for PCA concentrations - for each investigational RSV vaccine formulation

Finally, the immunogenicity index will be computed by taking the geometric mean of the 2 indexes:

$$DI = \sqrt{DI1 * DI2}$$

Overall desirability index

The overall desirability index will be obtained by computing the following weighted geometric mean: $D = DR^{0.4} * DI^{0.6}$

Finally, to address the robustness of the ranking, an evaluation of the uncertainty will be performed using a bootstrap approach.

• **SAMPLE SIZE EVALUATION THROUGH SIMULATION**

Two scenarios were envisaged with regards to immune response induced by the three RSV formulations (Table 24).

Table 24 Immunogenicity scenarios used for the desirability index simulations

Endpoint included in the desirability index	Formulation	Scenario 1	Scenario 2
RSV-A	30 PreF	10 log2	10 log2
	60 PreF	11 log2	10.5 log2
	120 PreF	12 log2	11 log2
PCA	30 PreF	100	100
	60 PreF	150	125
	120 PreF	200	150

Scenario 1 is assuming a higher increase of the immune response with the increased dose compared to scenario 2.

Two scenarios were also envisaged with regards to adverse event reactions induced by the three RSV formulations ([Table 25](#)).

Table 25 Reactogenicity scenarios used for the desirability index simulations

Endpoint included in the desirability index	Formulation	Scenario 1	Scenario 2
Grade 2/3 general AEs	30 PreF	25%	25%
	60 PreF	27.5%	35%
	120 PreF	30%	50%
Grade 2/3 fever	30 PreF	2%	4%
	60 PreF	3%	6%
	120 PreF	4%	10%

Scenario 2 is assuming a higher increase of the incidence of AEs with the increased dose compared to scenario 1.

These 4 combinations of scenarios were simulated 10000 times with a sample size of 95 evaluable subjects per group. The percentages for ranking each formulation at first place and for selecting the best one were computed and are described in the table below.

Table 26 Result of the ranking of the formulations following simulations of the different scenarios with a sample size of 95 subjects per group

Immuno scenario	Ranking #1 for immuno	Reacto scenario	Ranking#1 for reacto	Ranking #1 overall
1	120 PreF in 85.2% of simulations	1	30 PreF or 60 PreF in 90.2% of simulations	60 PreF or 120 PreF in 96.9% of simulations
		2	30 PreF in 91.2% of simulations	30 PreF or 60 PreF in 95.2% of simulations (4.8% for 120 PreF)
2	60 PreF or 120 PreF in 94% of simulations	1	30 PreF or 60 PreF in 90.2% of simulations	60 PreF or 120 PreF in 82.4% of simulations
		2	30 PreF in 91.6% of simulations	30 PreF or 60 PreF in 98.7% of simulations (1.3% for 120 PreF)

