5.2.2.2.1. Study group and treatment number allocation

The target will be to enrol approximately 400 eligible subjects who will be randomly assigned to four study groups in a (1: 1: 1: 1) ratio (approximately 100 subjects in each group).

Allocation of the subject to a study group at the investigator site will be performed using SBIR. The randomisation algorithm will use a minimisation procedure accounting for age (18 - 32 years or 33 - 45 years) and centre. Minimisation factors will have equal weight in the minimisation algorithm.

After obtaining the signed and dated ICF from the subject and having checked the eligibility of the subject, the site staff in charge of the vaccine administration will access SBIR. Upon providing the subject identification number, the randomisation system will determine the study group and will provide the treatment number to be used for the first dose.

The number of each administered treatment must be recorded in the eCRF on the Vaccine Administration screen.

When SBIR is not available, please refer to the SBIR user guide or the Study Procedures Manual (SPM) for specific instructions.

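### The two antibody models behind the ranking index name pre-vaccination titre as their only covariate, although allocation is minimised on age group and centre, so the lower limits may be slightly conservative

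*Protocol*

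**What the plan says.** Protocol Section 5.2.2.2.1 states: "The randomisation algorithm will use a minimisation procedure accounting for age (18 - 32 years or 33 - 45 years) and centre". The two factors carry equal weight, and subjects are "randomly assigned to four study groups in a (1: 1: 1: 1) ratio (approximately 100 subjects in each group").

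Section 10.8 refers the ranking to Appendix E. There, the RSV-A input is the "Geometric mean of neutralising antibody titres against RSV-A at Day 30 adjusted for pre-vaccination titres", and PCA is defined in the same way. The model is described as follows: "A response-surface model will be fitted on the log-transformed titre for each immune response (neutralising anti-RSV-A and PCA), including all RSV formulations". The index takes a confidence limit and not a point estimate: for DI1 the text reads "where LL is the lower limit of the 95% confidence interval of the GMT adjusted for pre-vaccination titres in log base 2", and DI2 also uses the lower limit of the adjusted mean. Each mention of adjustment in Appendix E refers to the pre-vaccination value. Age group and centre do not appear.

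For safety, "A logistic regression model will be fitted on each reactogenicity endpoint", and the estimated incidence rate itself goes into DR1 and DR2. The overall index is D = DR^0.4 × DI^0.6, and a bootstrap is planned to assess how robust the ranking is.

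**The concern.** A factor used to balance allocation normally belongs in the analysis model. If it is prognostic and left out, its variance stays in the error term and the reported precision is too low. In most trials the result is only a slightly conservative test. Here the lower confidence limit is the decision criterion, so a wider interval lowers DI1 and DI2 directly.

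The loss need not be the same for each formulation. The DI2 curve has slope 0.05 below 150 µg/mL and 0.025 above it, so equal loss of precision can cost formulations different amounts of desirability.

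The bootstrap could be affected too. If it resamples subjects within formulation, it breaks the balance on age and centre, and an unadjusted model would count that variation as ranking uncertainty. Appendix E does not give the resampling scheme, so this part is conditional.

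**Working it through.** **Inputs from the Protocol.** 95 evaluable subjects per group ("These 4 combinations of scenarios were simulated 10000 times with a sample size of 95 evaluable subjects per group"); the functions DI1, DI2, DR1, DR2 and D; the scenario values in Tables 24 and 25.

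**Inputs assumed because the Protocol gives none.** PCA residual SD 0.3 log10; RSV-A residual SD 1.5 log2 (range 1.0 to 2.0); share f of residual variance explained by age group and centre beyond baseline titre, 0 to 0.30; number of centres, 6 to 20.

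**1. The plan's own figures.** The reactogenicity column of Table 26 is the only one fixed by stated inputs. Simulating binomial counts at n = 95 through DR1 and DR2 puts 30 or 60 PreF first in 63.5% + 26.7% = 90.2% of runs in scenario 1 (stated 90.2%), and 30 PreF first in 91.0% in scenario 2 (stated 91.2% and 91.6%). The coded functions therefore match. The other columns also need an SD that is not stated, so they can be neither confirmed nor called wrong.

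**2. Standard error.** The overstatement is 1/√(1 − f): 1.026, 1.054 and 1.118 for f = 0.05, 0.10 and 0.20, that is 2.6%, 5.4% and 11.8%.

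**3. PCA at GMC 150.** LL = 150 × 10^(−1.96 × 0.3 × √(1 − f)/√95), and DI2 = 1/(1 + exp(0.05 × (150 − LL))).

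| f | LL | DI2 |
|---|---|---|
| 0 | 130.5 | 0.274 |
| 0.10 | 131.5 | 0.284 |
| 0.20 | 132.5 | 0.294 |

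DI2 rises by about 3% to 7%. It enters D with exponent 0.5 × 0.6 = 0.3, so D rises by about 1% to 2%.

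**4. Unequal effect across doses.** At f = 0.20, DI2 rises by about 6.4% at GMC 100, 7.1% at 150 and 2.3% at 200. Raised to the power 0.3, the changes in D are about +1.9%, +2.1% and +0.7%.

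**5. RSV-A.** With SD 1.5 log2 the half-width is 1.96 × 1.5/√95 = 0.302 log2. Multiplying by √(1 − f) gives 0.294, 0.286, 0.270 and 0.252 for f = 0.05, 0.10, 0.20 and 0.30. At a mean of 10 log2, DI1 moves from 0.574 to 0.577, 0.580, 0.585 and 0.592.

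**6. How the adjusted mean is weighted.** The limit belongs to each formulation's own mean, so the weights given to centres matter. Simulated analyses of covariance (three groups of 95, allocation balanced within age and centre, 12 centres of unequal size, SD 1.5 log2) gave these mean half-widths in log2:

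| f | Baseline only | + age, centre; observed margins | + age, centre; equal centre weights |
|---|---|---|---|
| 0 | 0.303 | 0.303 | 0.364 |
| 0.10 | 0.302 | 0.288 | 0.349 |
| 0.20 | 0.302 | 0.271 | 0.327 |

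Observed margins give the expected narrowing. Equal centre weights widen the interval even when the factors are prognostic. With 20 unequal centres and f = 0, observed margins cost almost nothing (0.303 to 0.305).

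**7. Effect on the ranking.** On the same simulated data with only the half-width changed, over SD 1.0 to 2.0 log2 and all four scenario combinations, the top-ranked formulation changes in at most 0.44% of runs at f = 0.05, 0.73% at f = 0.10 and 2.5% at f = 0.30.

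**The case against.** The strongest objection is that this argues from silence. Appendix E does not say that its covariate list is complete, and a full list is commonly left to the SAP, which is not at hand. In the text reviewed, the between-group part of Section 10.10 is also missing. This stands in part: one cannot say that the plan excludes age group and centre. But Section 10.8 makes Appendix E the governing text for the ranking. Appendix E does state an adjustment, repeatedly, and each time it is for pre-vaccination values alone. Section 10.10 would not change that.

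Second, the standard result on ignored balancing factors concerns differences between groups, while the limit here belongs to a single group's mean, and adjusting for centre can widen it. That is correct. It is why the fix must name the weighting.

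Third, a reader might infer that all the ranking models give intervals that are too wide. The documents do not support this: DR1 and DR2 use point estimates of incidence, so interval width plays no part there.

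Fourth, the effect on the decision is very small. The formulations have equal planned size, they shift in the same direction, and the index only guides selection. This stands, and it sets the weight of the point.

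**Conclusion.** The point holds as a minor improvement. As Appendix E is written, the RSV-A and PCA estimates are adjusted for pre-vaccination titre alone while allocation is minimised on age group and centre. If those factors predict Day 30 titre beyond baseline, the lower limits are slightly conservative: standard errors are about 3% to 12% too large when 5% to 20% of residual variance is explained. The same applies to the bootstrap if it resamples without keeping the balance. If the factors are not prognostic, nothing is lost or gained.

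The SDs, the explained variance and the centre counts are all assumptions. A reader might infer that the limits are certainly too low, or that the ranking is unreliable. Neither follows: the Protocol gives no prognostic strength for age or centre, and the first rank changes in under 1% of runs at up to 10% explained variance and in at most 2.5% at 30%.

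**What to change.** In Appendix E or the SAP, before any unblinded analysis by group:

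- Add age group (18–32 / 33–45 years) and centre, with small centres pooled by country, to the RSV-A and PCA models alongside pre-vaccination titre.
- Compute each formulation's adjusted mean and lower limit at the observed covariate margins, the same for all three formulations, and not with equal centre weights.
- Refit the same model in every bootstrap sample.
- If the factors are to stay out, give the reason.

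Adjusting the logistic model for Grade 2/3 general AEs is optional. The fever model is best left unadjusted: at the 2% to 10% rates in Table 25, 95 subjects give only about 2 to 10 events per group.

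The cost is wording, a few degrees of freedom and a pooling rule for small centres. No subjects, visits or data are added.

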10.4. Determination of sample size

The main objective of the study is to rank different formulations of the investigational RSV vaccine based on immunogenicity and safety/reactogenicity data up to 1 month post-vaccination (Day 30).

The sample size was determined to allow reliable ranking of the investigational RSV vaccine formulations based on a desirability index (see details in [APPENDIX E](#)) combining the following endpoints:

- Incidence rate of any Grade 2 and any Grade 3 general AE (solicited and unsolicited) and any vaccine-related SAE during the 7-day follow-up period after vaccination for each investigational RSV vaccine formulation.
- Incidence rate of Grade 2 and Grade 3 fever during the 7-day follow-up period after vaccination for each investigational RSV vaccine formulation.
- Neutralising antibody titres against RSV-A at 1 month post-vaccination.
- PCA concentrations at 1 month post-vaccination.

Different plausible scenarios (2 for immunogenicity and 2 for reactogenicity) were simulated several times and the desirability analysis for formulation selection was applied on each simulated data package, as described below.

Immunogenicity

1. The functional antibody response covers a range from 10 log₂ (30 PreF) to 12 log₂ (120 PreF) for neutralising RSV-A titres, and from 100 to 200 for the PCA concentrations.
2. The functional antibody response covers a range from 10 log₂ (30 PreF) to 11 log₂ (120 PreF) for neutralising RSV-A titres, and from 100 to 150 for the PCA concentrations.

Reactogenicity

1. The incidence rate varies between 25% (30 PreF) and 30% (120 PreF) for the Grade 2/3 general AEs, and between 2% and 4% for Grade 2/3 fever.
2. The incidence rate varies between 25% (30 PreF) and 50% (120 PreF) for the Grade 2/3 general AEs, and between 4% and 10% for Grade 2/3 fever.

These four combinations of scenarios were simulated 10000 times in SAS, with a sample size of 95 evaluable subjects per group (see details in [APPENDIX E](#)). The percentages for ranking each formulation at the first place and for selecting the best formulation were computed.

Simulations in SAS shows that a sample size of 100 subjects enrolled per group (N=95 evaluable subjects) allows to reach a percentage >80% for selecting one of the best formulations, i.e. with a high immune response and acceptable reactogenicity. Moreover, this sample size will allow to have a small percentage (<5%) for selecting formulations with an unacceptable reactogenicity.

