10.8. Analysis for ranking RSV formulations

A desirability approach will be used to rank the formulations and guide the formulation selection, based on safety/reactogenicity and immunogenicity data up to 1 month post-vaccination.

This method is a multi-criteria decision making approach based on desirability functions. The main idea is to identify for each endpoint a desirability function that associates any value to another one between 0 and 1 depending on its desirability ('0' being considered as not desirable at all and '1' as the most desirable). An index with values between 0 and 1 will be created for each endpoint. An overall desirability index can be calculated by computing a weighted geometric mean of the endpoint indexes. By definition, this overall index also takes values between 0 and 1 and characterises the level of desirability of any candidate formulation by a single value [Dewé, 2015].

The desirability index calculations will include reactogenicity and safety data up to Day 7 post vaccination (on the TVC) and immunogenicity data at 30 days post-vaccination (on the ATP cohort for immunogenicity up to Day 30). The formulations will be ranked based on the values obtained with this overall desirability index. Refer to [APPENDIX E](#) for more details on the desirability analysis.

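### The "<5%" chance of selecting a formulation with unacceptable reactogenicity is shown only when AE and fever rates are both bad; with one endpoint bad it is often exceeded

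*Protocol*

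**What the plan says.** Section 10.8 ranks the formulations by an overall desirability index on a 0 to 1 scale. Appendix E turns the Grade 2/3 general AE rate into DR1 and the Grade 2/3 fever rate into DR2. Of DR1 it says "This function will allocate a desirability value of 1, 0.5 and 0 to incidence rate equal to 0.1, 0.25 and 0.5 respectively", and of DR2 that "the function will allocate desirability values of 1, 0.5 and 0 to incidence rate equal to 0, 0.05 and 0.1 respectively". It then takes DR = sqrt(DR1 × DR2) and D = DR^0.4 × DI^0.6, where DI is the corresponding antibody index.

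Section 10.4 justifies the sample size by simulation: "These four combinations of scenarios were simulated 10000 times in SAS, with a sample size of 95 evaluable subjects per group". In Table 25 both reactogenicity scenarios move AEs and fever together (30/60/120 PreF):

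- Scenario 1: AEs 25/27.5/30%, fever 2/3/4%.
- Scenario 2: AEs 25/35/50%, fever 4/6/10%.

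Under scenario 2, Table 26 ranks 120 PreF first in 4.8% (immunogenicity scenario 1) and 1.3% (scenario 2). Section 10.4 concludes that "this sample size will allow to have a small percentage (<5%) for selecting formulations with an unacceptable reactogenicity".

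**The concern.** The conclusion in 10.4 covers any formulation with unacceptable reactogenicity. The evidence covers one that is at the bottom of both scales at once. A vaccine can raise fever without much change in other general AEs, or the reverse, and 120 µg has not been given to humans before (section 1.2.4), so its pattern is unknown.

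Ranking is the primary objective, this simulation justifies the sample size, and the ranking guides the choice of formulation for studies in pregnant women. If the protection is weaker when one endpoint is bad, a reader of 10.4 will put too much trust in a first-place ranking.

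**Working it through.** **Inputs.** The functions and weights are from Appendix E, antibody means from Table 24, rates from Table 25, and n = 95 per group from 10.4. The protocol gives no SDs. Assumed pairs (RSV-A SD in log2; PCA SD in natural-log units) are (1; 0.5), (1; 0.9), (2; 1.4) and (3; 2.1). Simplifications: one binomial rate and one log-normal mean per group instead of the fitted models, and lower limit = mean − 1.96 × SD/√95. Fever is drawn either independently of the AEs or nested within them, since fever is itself a solicited general AE. There are 100,000 simulated trials per setting.

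**Reproducing Table 26.** Reactogenicity ranking needs no SD. For scenario 1, 30 or 60 PreF comes first in about 90% (stated 90.2%). For scenario 2, 30 PreF comes first in about 91% (stated 91.2% and 91.6%). At SDs (3; 2.1), 120 PreF is first on immunogenicity scenario 1 in 85.8% (stated 85.2%). With both endpoints bad and independent fever, it is first overall in 4.3% and 1.6% (stated 4.8% and 1.3%). Not every cell matches: immunogenicity 2 with reactogenicity 1 gives 89% for 60 or 120 PreF, against 82.4%.

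**One endpoint bad.** Percentage of trials ranking 120 PreF first, over the four SD pairs:

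| Setting | Fever | Immunogenicity 1 | Immunogenicity 2 |
|---|---|---|---|
| Both bad (Table 25 scenario 2) | independent | 1.7-4.3 | 0.8-1.6 |
| | nested | 2.7-5.5 | 1.5-2.2 |
| Fever 4/6/10%, AEs 25/27.5/30% | independent | 18.1-24.2 | 15.3-15.7 |
| | nested | 20.1-25.9 | 17.3-18.0 |
| AEs 25/35/50%, fever 2/3/4% | independent | 5.6-17.3 | 3.0-6.9 |
| | nested | 6.4-18.4 | 3.6-7.6 |

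If only the 120 PreF arm departs from scenario 1, over a similar SD range, fever at 10% gives 9.6-15.5% and 9.0-10.0%. AEs at 50% give 1.6-8.0% and 1.1-3.5%.

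**Cause.** The end values are DR1(0.5) = 1/(1 + e^6.25) = 0.0019 and DR2(0.1) = 1/(1 + e^6) = 0.0025. Each component has exponent 0.4 × 0.5 = 0.2 in D, so they enter as 0.0019^0.2 = 0.286 and 0.0025^0.2 = 0.301. Three checks show whether this explains the excess.

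1. At the exact planned rates and antibody means (immunogenicity 1), D for 30/60/120 PreF is 0.339/0.476/0.205 with fever bad and 0.356/0.462/0.250 with AEs bad. 120 PreF is last both times.
2. Forcing D to 0 when the estimated AE rate is at least 0.5 or the fever rate at least 0.1 changes the independent-fever figures little. Fever alone becomes 17.9-23.7% and 15.2-15.4%; AEs alone become 5.6-14.6% and 3.0-6.2%. No change exceeds 3 points.
3. Holding the rates at their true values, with error only in the antibodies, cuts fever alone to 0-2.6% and 0-0.8%. AEs alone fall to 0-2.4% and 0-0.6% for the first three SD pairs. At (3; 2.1) they remain at 12.4% and 3.5%, so antibody error contributes there.

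The fever curve shows why. A true rate of 10% has a standard error of √(0.1 × 0.9/95) = 3.1 points. Six fevers in 95 (6.3%) give a factor DR2^0.2 of 0.70, and ten (10.5%) give 0.27. Six or fewer occur with probability 0.15 when the true rate is 10%.

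**The case against.** A reader might infer that the printed zeros are the fault: a true zero in a geometric mean excludes a candidate, whereas 0.002 leaves about 30% of the credit for antibodies to buy back. The documents do not support this as the explanation. Every curve in Appendix E is a logistic described by its rounded ends: DR1(0.1) = 0.9994 and DR2(0) = 0.9975 are printed as 1, and DI2(25) = 0.0019 and DI1(6) = 0.005 as 0. The formulas are given in full, and neither 10.8 nor Appendix E says that 0 is a veto. The first two checks above show that truncation hardly changes the result. It would also let one subject decide elimination (9 fevers in 95 keep a factor of 0.34, and 10 would give 0), and arms beyond a cut-off would tie at 0.

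It is also too strong to say that the figure holds only when both endpoints are bad. Some AE-only settings stay below 5%.

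In the plan's defence, the 10.4 sentence follows directly on the simulation description, and Table 26 prints the exact cells. The index only guides selection. A bootstrap of the ranking and between-group AE comparisons are planned, and 120 PreF would need a further Phase II study in pregnant women before Phase III. These limit the consequences. They do not make the general statement in 10.4 supported.

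The absolute percentages depend on the unknown SDs. With PCA varying on an additive scale (SD 100-500), both-bad results were 1.3-15.6% and one-bad results 6-38%. The level is uncertain, but the one-endpoint excess remains.

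**Conclusion.** The point holds in a limited form. Section 10.4 states in general terms a property that Tables 25 and 26 show only for 50% AEs and 10% fever together. With fever alone bad, the chance of ranking 120 PreF first is about 18-26% and 15-18% on the Table 25 rates, and above 5% in every setting tried. With AEs alone bad it is about 6-18% and 3-8%, so it may or may not exceed 5%. These figures assume RSV-A SD 1-3 log2 and PCA SD 0.5-2.1 natural-log units, with simple per-group estimates in place of the planned models.

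The excess comes mainly from sampling error in rates estimated on 95 subjects and passed through steep curves, with antibody error adding to it at the largest SDs. The index functions need not change, and the sample size is not shown to be wrong. What needs correcting is the claim made for it.

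**What to change.** 1. In section 10.4, limit the statement to a formulation with 50% Grade 2/3 general AEs and 10% Grade 2/3 fever together.
2. Add two combinations to Tables 25 and 26, each with both immunogenicity scenarios: fever scenario 2 with AE scenario 1, and AE scenario 2 with fever scenario 1. Report how often 120 PreF is ranked first, from the sponsor's own simulation, and state the SDs used.
3. In Appendix E, describe the reactogenicity end values as approximately 0 (about 0.002), and leave the functions untruncated.

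The cost is a re-run of existing code with four more cells, two wording changes and a less favourable stated figure. Data collection and the ranking method are unaffected.

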8.1.3.2. Solicited general adverse events

The following local (injection-site) AEs will be solicited:

Table 16 Solicited general adverse events

Fatigue
Fever*
Gastrointestinal symptoms†
Headache

* Fever is defined as temperature $\geq 37.5^{\circ}\text{C}$ for oral, axillary or tympanic route, or $\geq 38.0^{\circ}\text{C}$ for rectal route. The preferred route for recording temperature in this study will be oral.

† Gastrointestinal symptoms include nausea, vomiting, diarrhoea and/or abdominal pain.

Note: Temperature will be recorded in the evening. Should additional temperature measurements be performed at other times of day, the highest temperature will be recorded in the eCRF.

8.1.4. Clinical laboratory parameters and other abnormal assessments qualifying as adverse events or serious adverse events

In absence of diagnosis, abnormal laboratory findings (e.g. clinical chemistry, haematology, urinalysis) or other abnormal assessments that are judged by the investigator to be clinically significant will be recorded as AE or SAE if they meet the definition of an AE or SAE (refer to Sections 8.1.1 and 8.1.2). All Grade $\geq 3^*$ abnormal laboratory findings should be reported as AE/SAE. Clinically significant abnormal laboratory findings or other abnormal assessments that are present at baseline and significantly worsen following the start of the study will also be reported as AEs or SAEs. If a diagnosis is associated with the abnormal findings, the diagnosis should be reported as AE/SAE.

The investigator will exercise his or her medical and scientific judgement in deciding whether an abnormal laboratory finding or other abnormal assessment is clinically significant.

**Grading will be based on the Food & Drug Administration (FDA) Guidance for Industry "Toxicity Grading Scale for Healthy Adult and Adolescent Volunteers Enrolled in Preventive Vaccine Clinical Trials" [APPENDIX D]*

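### Table 26 was evidently simulated as if Grade 2/3 fever and Grade 2/3 general AEs were independent, although fever is one of the general AEs; with the overlap, the under-5% mis-selection claim in Section 10.4 is not supported

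*Protocol*

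**What the plan says.** Appendix E defines the first reactogenicity endpoint as "Incidence rate of any Grade 2 and any Grade 3 general AE (solicited and unsolicited) and any vaccine-related SAE" over the 7-day follow-up. The second is the rate of Grade 2 and Grade 3 fever over the same period. Each rate is turned into a desirability (DR1 and DR2), and the reactogenicity index is the geometric mean of the two. Section 8.1.3.2, in "Table 16 Solicited general adverse events", lists fatigue, fever, gastrointestinal symptoms and headache.

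Table 25 gives a rate for each endpoint, formulation and scenario. On the simulation itself Appendix E says: "These 4 combinations of scenarios were simulated 10000 times with a sample size of 95 evaluable subjects per group". It does not say how the two reactogenicity endpoints were generated jointly, and it gives no SD for the immunogenicity endpoints.

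Table 26 reports the results. With immunogenicity scenario 1 and reactogenicity scenario 2, the overall first rank goes to "30 PreF or 60 PreF in 95.2% of simulations (4.8% for 120 PreF"). Section 10.4 concludes that the sample size gives a "small percentage (<5%) for selecting formulations with an unacceptable reactogenicity".

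**The concern.** Under the protocol's definitions a Grade 2/3 fever is always also a Grade 2/3 general AE, so one subject's fever enters both DR1 and DR2. The two observed rates in an arm are then positively correlated. An arm that looks mild by chance tends to look mild on both components, and the errors reinforce each other. If the two endpoints are drawn independently, the errors partly cancel, the reactogenicity index looks more precise than it will be, and the ranking looks more reliable than it is.

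At stake is the safety half of the sample-size justification: the chance that 120 PreF ranks first when it is assumed to be clearly more reactogenic. The supporting figure, 4.8%, lies only 0.2 points under the stated limit, so a small error is enough to remove the claim. Section 1.2.4 notes that this study gives the 120 µg formulation to humans for the first time, so readers will rely on that sentence.

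**Working it through.** **Inputs from the protocol.** There are 95 evaluable subjects per group and 10,000 runs. The Table 25 rates for 30/60/120 PreF are:

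| | General AEs, Grade 2/3 | Fever, Grade 2/3 |
|---|---|---|
| Reactogenicity scenario 1 | 25 / 27.5 / 30% | 2 / 3 / 4% |
| Reactogenicity scenario 2 | 25 / 35 / 50% | 4 / 6 / 10% |

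DR1 = 1/(1+exp(−50(0.25−IR))) for IR ≤ 0.25, with 25 in place of 50 above 0.25. DR2 = 1/(1+exp(−120(0.05−IR))). DR = √(DR1·DR2). A logistic model with group as a factor returns the observed proportions, so IR is taken as events/95.

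**Step 1: size of the overlap.** If fever (rate f) is a subset of general AEs (rate g), the within-arm correlation is f(1−g)/√[f(1−f)g(1−g)].
- Scenario 1, 30 PreF: 0.02×0.75/√(0.02×0.98×0.25×0.75) = 0.25.
- Scenario 2, 120 PreF: 0.10×0.50/√(0.10×0.90×0.50×0.50) = 0.33.

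Across the six arms it runs from 0.25 to 0.35.

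**Step 2: reproduce the reactogenicity column.** No undisclosed input is needed. The binomial counts were enumerated exactly, with ties split. In the nested case the fever count is binomial among the general-AE subjects with probability f/g, which keeps both Table 25 rates.

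| Ranked first on reactogenicity | Printed | Independent | Nested |
|---|---|---|---|
| Scenario 1: 30 or 60 PreF | 90.2% (both rows) | 89.99% | 88.36% |
| Scenario 2: 30 PreF | 91.2% and 91.6% | 91.19% | 88.76% |

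The Monte Carlo SE at 10,000 runs is √(0.902×0.098/10000) = 0.30 points in scenario 1 and 0.28 points in scenario 2.
- Independent draws: scenario 1 misses by 0.21/0.30 = 0.7 SE. Scenario 2 misses by 0.0 and by 0.41/0.28 = 1.5 SE.
- Nested draws: scenario 1 misses by 1.84/0.30 = 6 SE. Scenario 2 misses by 2.44/0.28 = 9 SE and 2.84/0.28 = 10 SE.

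**Step 3: precision of the 4.8%.** SE = √(0.048×0.952/10000) = 0.21 points, so the 95% interval is 4.8 ± 1.96×0.21, about 4.4% to 5.2%. Even under independence the figure does not clearly separate from 5%.

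**Step 4: effect on the overall ranking.** The overall index is D = DR^0.4 × DI^0.6, so the immunogenicity spread is needed, and the protocol does not give it. It was assumed and varied: RSV-A SD 1 to 8 log2, PCA SD 0.5 to 5 log2 or 50 to 400 on the raw scale, correlation 0, 0.5 or 0.95, and group-specific, dose-linear or log-dose immunogenicity models. That makes 3×(9+7)×7×3 = 1,008 settings, at 30,000 runs each.

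The 92 settings that give 4.5% to 5.1% for 120 PreF first under independence (immunogenicity 1, reactogenicity 2), bracketing the printed 4.8%, give 5.4% to 6.7% when fever is nested, with a median of 6.1%. All 92 exceed 5%. The usual increase is about 1 to 1.5 points.

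**The case against.** The strongest objection is that the overall 4.8% cannot be rebuilt from the protocol. The SDs, the correlation and the covariate structure are missing, and no setting tried reproduces all six immunogenicity and overall cells; in the grid above the best still misses one by about 4 points. Settings tuned to 4.8% tend to give about 1.8% to 2.0% under independence for immunogenicity 2 with reactogenicity 2, where 1.3% is printed (SE about 0.11 points). Settings that do hit 1.3% give about 3.5% to 3.8% under independence and 4.7% to 5.0% nested. RSV-A SDs of several log2 units also look wide against the titre categories in Section 10.10. This stands. A reader might infer that the true figure is 6%, and the documents do not support that. They support a direction, an approximate increment, and an anchor at the printed 4.8%. The settings that stay at or below 5% when nested do so by starting about a point below the figure the protocol prints.

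A second objection is that the Table 25 general-AE rates might mean AEs other than fever, with the endpoint formed as the union with fever. Exact enumeration then gives 90.85% and 90.45%, about 2 to 4 SEs from the printed values, and the share for 120 PreF is about 4.2% to 4.9%, which would keep the claim. This reading is less literal, because Table 25 labels its rows as endpoints of the index and the index endpoint includes fever, and it fits worse than independence. It is not fully excluded, so a reader who infers that Table 26 can only have come from independent draws goes further than the evidence.

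Third, the effect is small. Section 10.4 describes assumed scenarios, not a controlled error rate. The actual ranking uses observed rates whatever the planning simulation assumed, and Appendix E adds a bootstrap for its uncertainty. This is correct, and it limits the point to the stated justification.

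**Conclusion.** The point holds for the planning simulation. The endpoint definitions make Grade 2/3 fever a subset of the first endpoint, and the reactogenicity column of Table 26 matches independent generation to Monte Carlo precision. Nesting at the Table 25 rates lowers that column by about 1.8 points in scenario 1 and 2.4 to 2.8 points in scenario 2.

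For the overall ranking, the chance that 120 PreF comes first under immunogenicity 1 with reactogenicity 2 moves from the printed 4.8% to roughly 5.4% to 6.7%. That range assumes the Table 25 rates apply to the endpoints as defined, that the printed 4.8% came from independent draws, and that the unstated SDs lie among the settings consistent with it. On that footing the under-5% statement is not supported.

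A reader might go on to infer that the sample size is inadequate or the ranking analysis invalid. Neither follows. The claim of more than 80% for picking one of the best formulations, whose lowest printed value is 82.4%, moves by less than about 0.5 points.

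**What to change.** Rerun the existing simulation with fever generated as a subset of Grade 2/3 general AEs, keeping the Table 25 rates and using the sponsor's own immunogenicity SDs and correlation. State the joint generation and those SDs in Appendix E. If the Table 25 general-AE rates were meant to exclude fever, say so and give the resulting endpoint rates. Replace the reactogenicity and overall entries in Table 26; the immunogenicity column is unaffected. Restate the mis-selection sentence in Section 10.4 with whatever figure results. Do not write in 6%, since that depends on SDs assumed here.

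The cost is one rerun and a few edited lines. The number of subjects and the trial analysis stay as they are. The only downside is a slightly less favourable stated figure.
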